#### 12.6 Pharmacodynamic Data

- *Lipid Parameters:* LDL-C, Total Cholesterol, non-HDL-C, HDL-C, VLDL-C, and Triglycerides
- Retinoid pathway markers: retinol, retinol binding protein

- *NASH biomarkers*: ELF [Hyaluronic acid (HA), Procollagen III amino terminal peptide (PIIINP), Tissue inhibitor of metalloproteinase 1 (TIMP-1)], cytokeratin-18, PRO-C3, IL-1β, IL-6, IL-10, INF-gamma, and TNF-α
- *Immunogenicity:* Specified subjects will be assessed for anti-drug antibodies.
- *Genotype:* All patient cohorts will be assessed for HSD17B13 and PNPLA3 gene variants with the subject's written consent.
- *Exosomal analysis:* Blood will be drawn for exosomal analysis of *PNPLA3* and *HSD17B13* if technically feasible.
- *MRI-PDFF*: Liver fat content via MRI-PDFF will be evaluated and quantified. Change from baseline will be measured.
- *FibroScan*®: Per the Schedule of Assessments, pre-dose and post-dose liver stiffness baseline will be measured.
- *Liver Biopsy*: Samples from biopsies collected following multiple doses of ARO-HSD at different dose levels will undergo analysis for HSD17β13 mRNA knockdown and evaluation in PNPLA3 mRNA expression. HSD17B13 and PNPLA3 protein expression may be assessed if scientifically feasible.

# 12.7 Data Recording and Quality Control

Source documents must be maintained for each participant in the study, consisting of all demographic and medical information, including clinical laboratory data, etc. A copy of the signed informed consent form must be retained. All information on the eCRFs must be traceable to these source documents in the participant's file.

Data recorded in all participants' eCRFs will be subjected to a quality control review.

#### 13. STUDY APPROVAL AND CONDUCT

The following conditions will be met.

#### 13.1 Regulatory Approval

The requirements for the conduct of clinical trials in accordance with local applicable regulations will be met before commencement of this study.

# 13.2 Ethics Committee (EC)/ Institutional Review Board (IRB) Approval

Prior to initiation of the study, written EC/IRB approval of the Protocol and Informed Consent Forms, based on the principles of ICH cGCP procedures, will be received. A copy of the signed and dated letter of approval will be provided to the clinical site and Arrowhead Pharmaceuticals, Inc. prior to study commencement. Any written information and/or advertisements to be used for volunteer recruitment will be approved by the EC/IRB prior to use. A list of the EC/IRB

voting members, their titles or occupations, FWA number (where applicable) and their institutional affiliations will be requested before study initiation.

Protocol modifications that may impact patient safety or the validity of the study will be approved by the IRB, following written agreement from the Sponsor.

## 13.3 Ethical Considerations

This study will be carried out per the Declaration of Helsinki 1964, as modified by the 64th World Medical Assembly, Fortaleza, Brazil, October 2013, the Notes for Guidance on Good Clinical Practice (cGCP) (2000) (CPMP/ICH/135/95), and the Principles of the ICH cGCP. The protocol will be submitted for approval to the EC/IRB, and written approval obtained before subjects are enrolled. The composition of the EC/IRB will also be provided to the Sponsor. If approval is suspended or terminated by the IRB, the PI will notify the Sponsor immediately

Where applicable, the clinical site and Arrowhead Pharmaceuticals, Inc. agree to abide by the local compensation guidelines for injury resulting from participating in a company-sponsored research project. Compensation will only be provided on the understanding that the provision of compensation does not amount to an admission of legal liability and is subject to the proposed recipient signing a full and complete release of the company from all claims, damages and costs.

#### 13.4 Written Informed Consent

Informed consent will be obtained before the patient can participate in the study. The contents and process of obtaining informed consent will be in accordance with all applicable regulatory requirements. Study participation includes all screening procedures, as well as any wash-out of excluded medications.

It is the responsibility of the PI (or medically qualified designee) to obtain a written informed consent from everyone participating in this study after adequate explanation of the aims, methods, objectives, and potential hazards of the study. The PI (or medically qualified designee) must also explain to the participants that they are completely free to refuse to enter the study or to withdraw from it at any time. Appropriate forms for documenting a written consent will be provided by the PI or by Arrowhead Pharmaceuticals, Inc.

For this study, each eligible participant will be required to provide written informed consent before participation in the study.

All eligible participants will have the study explained by the PI or designee. They will receive a full explanation, in lay terms, of the aims of the study, the discomforts, risks and benefits in taking part as well as of insurance and other procedures for compensation in case of injury. It will be explained that the study is for research purposes only and is not expected to provide any therapeutic benefit to the individual. It will be pointed out that they can withdraw from the study at any time without prejudice. Each participant will acknowledge receipt of this information by giving written informed consent for participation in the study. The volunteer will be given a copy of the signed Informed Consent Form to retain.

# 13.5 Emergency Contact with Principal Investigator

Suitable arrangements will be made for participants to contact the PI or medically trained designee in the event of an emergency.

#### 13.6 Notification of General Practitioner

It is the responsibility of the PI or designee, to notify, where applicable, with the consent of the participant, the general practitioner of the patient's participation in the trial, by sending a letter stating the nature of the trial, treatments, expected benefits or adverse events and concomitant drugs to be avoided.

# 13.7 Clinical Laboratory Certification and Reference Ranges

Before the initiation of this study, the PI, or designee, will obtain a copy of the certification form, with certification number and expiration date for all clinical laboratories (excluding central laboratories) used in the study. Reference ranges for each clinical laboratory test used in this study will be obtained from the appropriate laboratory, which will perform the test for the study.

#### 13.8 **Protocol Deviations**

A protocol deviation is defined as any intentional or unintentional change to, or noncompliance with, the approved protocol procedures or requirements. The PI will conduct the study in compliance with the approved protocol and will not implement any deviation from or changes to the protocol without prior agreement by the Sponsor and review and documented approval from the EC/IRB of an amendment, except where necessary to eliminate an immediate hazard to study patients.

Deviations may result from the action or inaction of the participant, PI, or site staff. Examples of deviations include, but are not limited to:

- Failure to adhere to study exclusion and inclusion criteria
- Failure to comply with dispensing or dosing requirements
- Use of medications, food, drink, herbal remedies, or supplements that are specifically prohibited in the protocol
- Missed or out-of-window visits
- Drug dosing not administered within the time frame specified in the protocol
- Failure to adhere to test requirements, including vital signs, laboratory tests, physical examinations, PK blood draws, medical history, etc. either tests not done, incorrect tests done, or not done within the time frame specified in the protocol

Protocol deviations impacting patient safety or eligibility will be reported to the Sponsor or CRO within 2 business days of occurrence and to the EC/IRB /competent regulatory authority per local regulatory requirements.

The PI is responsible for ensuring that any known protocol deviations are recorded and reported as agreed.

# 13.9 Termination of the Study

The Sponsor reserves the right to discontinue the trial at any time. Reasons will be provided in the event of this happening. The PI reserves the right to discontinue the study for safety reasons at any time in collaboration with the Sponsor.

#### 14. STUDY ADMINISTRATION

# 14.1 Study Monitoring

Arrowhead Pharmaceuticals, Inc. is responsible for assuring the proper conduct of the study about protocol adherence and validity of the data recorded on the eCRFs. Participant confidentiality will be maintained.

In accordance with applicable regulations, cGCP, and Arrowhead Pharmaceuticals, Inc. procedures, Arrowhead Pharmaceuticals, Inc. will be responsible for assigning a study monitor (CRA) who will contact the site to organize a visit prior to participant enrolment to review the protocol and data collection procedures with site staff. In addition, the assigned study monitor will periodically contact the site, including conducting on-site visits. The extent, nature and frequency of on-site visits will be based on such considerations as the study objective and/or endpoints, the purpose of the study, study design complexity, and enrolment rate.

During these site visits, the study monitor will:

- Check the progress of the study
- Review study data collected
- Conduct source document verification
- Identify any issues and address their resolution
- Check investigational product accountability
- Review blood and urine samples and ensure they are labeled and stored correctly

This will be done to verify that the:

- Data are authentic, accurate and complete.
- Safety and rights of participants are being protected.
- Study is conducted in accordance with the currently approved protocol (and any amendments), cGCP and all applicable regulatory requirements.

The PI agrees to allow the monitor direct access to all relevant documents and to allocate his/her time and the time of his/her staff to the monitor to discuss findings and any relevant issues.

At study closure, a study monitor will conduct the following activities in conjunction with the PI or site staff as appropriate:

- Return of all study data to Arrowhead Pharmaceuticals, Inc
- Data queries
- Accountability, reconciliation and arrangements for unused investigational product(s)

- Inventory and final disposition (e.g., destruction, shipping to repository, etc.)
- Review of site study records for completeness

# 14.2 Quality Assurance

To ensure compliance with cGCP and all applicable regulatory requirements, Arrowhead Pharmaceuticals, Inc. may conduct a quality assurance audit of the study site. Regulatory agencies may also conduct a regulatory inspection of this study. Such audits/inspections can occur at any time during or after completion of the study. If an audit or inspection occurs, the PI and clinical site agree to notify Sponsor as soon as possible following awareness of an impending regulatory inspection. The PI and clinical site agree to allow the auditor/inspector direct access to all relevant documents and allocate his/her time and the time of his/her staff to the auditor/inspector to discuss findings and any relevant issues.

#### 14.3 Records Retention

Following closure of the study, the PI must maintain all site study records in a safe and secure location. The records must be maintained to allow easy and timely retrieval, when needed (e.g., audit or inspection) and whenever feasible, to allow any subsequent review of data in conjunction with assessment of the facility, supporting systems and staff. When permitted by local laws/regulations or institutional policy, some of these records can be maintained in a format other than hard copy (e.g., microfiche, scanned, electronic); however, caution needs to be exercised before such action is taken. The PI must assure that all reproductions are legible and are a true and accurate copy of the original and meet accessibility and retrieval standards, including re-generating a hard copy, if required. Furthermore, the PI must ensure there is an acceptable back-up of these reproductions and that an acceptable quality control process exists for making these reproductions.

Arrowhead Pharmaceuticals, Inc. will inform the PI of the time period for retaining these records to comply with all applicable regulatory requirements. The minimum retention time will meet the strictest standard applicable to that site for the study, as dictated by any institutional requirements or local laws or regulations, or Arrowhead Pharmaceuticals, Inc. standards/procedures; otherwise, the retention period will default to 15 years.

The material to be stored shall include, but is not limited to, the following:

- Signed and dated copy of the final study protocol and any amendments
- Signed and dated letter of IRB approval, letter of constitution of the IRB and copies of any other correspondence relevant to the study with the IRB or regulatory authorities
- The IRB approved Informed Consent Form
- Current *curriculum vitae* (signed and dated) of the Principal Investigator and co-workers with major responsibilities in the trial
- Site Signature and Delegation of Responsibility Log
- FDA Form 1572 (where applicable)
- Financial Disclosure Form(s)
- Blank CRF/eCRF

- Signed participant informed consent forms
- Laboratory reference ranges (signed and dated)
- The completed CTN Application Form (where applicable)
- Clinical raw data including the Source Data Forms, all clinical laboratory report forms, patient CRFs, drug accountability forms, and dispensing records, etc

# 15. INFORMATION DISCLOSURE AND INVENTIONS

# 15.1 Ownership

# 15.2 Confidentiality

#### 15.3 **Publication**

# 16. APPENDICES

# 16.1 Study Modification Guidelines For Subjects And Patients With Baseline Pre-Dose Evidence Of Liver Disease

Treatment-Emergent ALT	Treatment-Emergent Total Bilirubin (TBL)	Liver Symptoms	Action
Normal baseline with treatment emergent (TE) increase to ALT > 5x ULN  Elevated baseline with TE increase to: ALT > 3x baseline or > 300 U/L (whichever occurs first)	Normal	None	Repeat ALT, AST, ALP, TBL, in 2–3 days Follow-up for symptoms.
Normal baseline with TE increase to ALT > 8x ULN  Elevated baseline with TE increase to: ALT > 5x baseline or > 500 U/L (whichever occurs first)	Normal	None	Interrupt study drug. Initiate close observation and workup for competing etiologies. (see below)  Study drug can be restarted only if an alternative etiology is identified and liver enzymes return to baseline.
Normal baseline with TE increase to ALT > 3x ULN  Elevated baseline with TE increase to ALT > 2x baseline or > 200 U/L (whichever occurs first)	TBL > 2x ULN	None	Interrupt study drug. Initiate close observation and workup for competing etiologies.  Study drug can be restarted only if an alternative etiology is identified and liver enzymes return to baseline.

Normal baseline with	Normal or elevated	Symptoms of	Interrupt study drug.
TE increase to ALT		clinical	Initiate close observation
> 3x ULN		hepatitis -	and workup for
		severe fatigue,	competing etiologies.
Elevated baseline with		nausea,	
TE increase to ALT >		vomiting,	Study drug should not
2x baseline or $> 200$		right upper	be restarted
U/L		quadrant	
(whichever occurs first)		pain	

Source: Adapted from Chalasani, Naga and Regev, Arie et al. Drug-Induced Liver Injury in Subjects with Preexisting Chronic Liver Disease in Drug Development: How to Identify and Manage? Gastroenterology, Volume 151. Issue 6, 1046 – 1051

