BMI (Height and Body Weight)	X	$X^1$							$\mathbf{X}^{1}$		$X^1$		$X^1$	
Concomitant Meds/Therapies	X	X					X	X	X	X	X	X	X	
Electrocardiogram (See Section 10.3.3)	X	X			X	X	X		$(0, 1, 2hr)^2$				X	
Urine Pregnancy Test (WOCP) confirmed negative pre-dose/pre-bx	X	X							pre-dose		pre-bx		X	
FSH (post-menopause)	X													
Urine Drug Screen	X													
Vitals (BP, temp, HR, RR, O 2 )	X	X		X	X	X	X	X	X	X	X	X	X	
HIV, Hep B, C	X													
Labs (heme, coag, chem, lipase, lipids)	X	X					X	X	X	X	X	X	X	
Retinol, RBP, blood for exosomes, cytokine panel		X						X	X	X	X	X	X	
Hemoglobin A1c	X	X											X	
Pro-C3, ELF, Cytokeratin-18		X											X	
Blood PK		X		X	X	X	X	X	pre-dose					
Genotyping (HSD17β13, PNPLA3)	X													
Urinalysis	X	X					X	X	X	X	X	X	X	
Liver Biopsy, FibroScan, MRI-PDFF	X 										X			
Administration of ARO-HSD			X						X					

<sup>1 Body weight only  10-minute window allowed

<sup>3 Liver biopsy can be done at D1, as long it is completed prior to any D1 procedures Version 7.0, 12 March 2021

Arrowhead Pharmaceuticals, Inc. Protocol No.: AROHSD1001

Confidential

Page 11 of 59

Anti-Drug Antibodies		X				X		X	
Adverse Events Collection	х –							X	
Pregnancy phone call									X

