## 7.4 **Stopping Rules**

A decision to stop the trial early or discontinue drug in an individual subject, group of subjects or to halt enrollment temporarily or permanently may be indicated based on any of the following:

- 1. A serious adverse reaction (i.e. an SAE considered at least possibly related to the IMP administration) in ONE subject; or severe non-serious adverse reactions (i.e. severe non-SAEs considered as, at least, possibly related to the IMP administration) in TWO subjects in the same cohort, independent of whether or not the events occur within the same system-organ-class.
- 2. One of the following abnormal results at least possibly related to ARO-HSD:
  - In NHV cohorts:
    - o Treatment emergent AST and/or ALT > 8X ULN which must be confirmed by repeat blood draw within 48 hours of initial results, OR

- A treatment emergent AST or ALT >3X ULN (must be confirmed on repeat) with a total bilirubin >2X ULN (must be confirmed on repeat), OR
- A treatment emergent ALT or AST >3X ULN (must be confirmed on repeat) with symptoms of RUQ pain, fever, rash or eosinophilia, OR
- A treatment emergent AST or ALT >3X ULN (must be confirmed on repeat) with an INR > 1.5 (must be confirmed on repeat) and which must not be explained by another plausible cause
- See Appendix 16.1 for treatment modification guidelines in patients with baseline/pre-dose elevated ALT or AST.

If such serious adverse reactions or severe non-serious adverse reactions occur as outlined above, enrollment and dosing in healthy volunteers will be paused pending a review of safety data and a decision on how to proceed by the DSC.

The Sponsor or PI can discontinue any patient at any time with or without DSC consultation. If such events (as described above) occur and the patient is not discontinued from the study, the reason for not discontinuing the patient will be included in DSC meeting minutes. Including, but not limited to the events listed above, the DSC may pause the study to additional dosing or dose escalation to provide time to evaluate safety data and recommend the action to be taken, which may include, but is not limited to, one of the following:

- 1. Discontinuation of a patient or group of patients from the study.
- 2. The study is stopped immediately with no further dosing
- 3. The study will continue until the current cohort is completed.

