12. APPENDIX

12.1 Appendix A: Grading Laboratory Values according to CTCAE Version 5

	Grade 1	Grade 2	Grade 3	Grade 4
Serum Chemistry				
Alanine aminotransferase, increased	Normal baseline: > ULN – 3.0 x ULN Abnormal baseline: 1.5 x – 3.0 x baseline	Normal baseline: > 3.0 x – 5.0 x ULN Abnormal baseline: > 3.0 x – 5.0 x baseline	Normal baseline: > 5.0 x – 20.0 x ULN Abnormal baseline: > 5.0 x – 20.0 x baseline	Normal baseline: > 20.0 x ULN Abnormal baseline: > 20.0 x baseline
Alkaline Phosphatase, increased	Normal baseline: > ULN – 2.5 x ULN Abnormal baseline: 2.0 x – 2.5 x baseline	Normal baseline: > 2.5 x – 5.0 x ULN Abnormal baseline: > 2.5 x – 5.0 x baseline	Normal baseline: > 5.0 x – 20.0 x ULN Abnormal baseline: > 5.0 x – 20.0 x baseline	Normal baseline: > 20.0 x ULN Abnormal baseline: > 20.0 x baseline
Aspartate aminotransferase, increased	Normal baseline: > ULN – 3.0 x ULN Abnormal baseline: 1.5 x – 3.0 x baseline	Normal baseline: > 3.0 x – 5.0 x ULN Abnormal baseline: > 3.0 x – 5.0 x baseline	Normal baseline: > 5.0 x – 20.0 x ULN Abnormal baseline: > 5.0 x – 20.0 x baseline	Normal baseline: > 20.0 x ULN Abnormal baseline: > 20.0 x baseline
Creatine phosphokinase, increased	> ULN – 2.5 x ULN	> 2.5 – 5.0 x ULN	> 5 – 10 x ULN	> 10 x ULN
Gamma glutamyl transferase, increased	Normal baseline: > ULN – 2.5 x ULN Abnormal baseline: 2.0 x – 2.5 x baseline	Normal baseline: > 2.5 x – 5.0 x ULN Abnormal baseline: > 2.5 x – 5.0 x baseline	Normal baseline: > 5.0 x – 20.0 x ULN Abnormal baseline: > 5.0 x – 20.0 x baseline	Normal baseline: > 20.0 x ULN Abnormal baseline: > 20.0 x baseline
Total bilirubin, increased	Normal baseline: > ULN – 1.5 x ULN Abnormal baseline: > 1.0 x – 1.5 x baseline	Normal baseline: > 1.5 x – 3.0 x ULN Abnormal baseline: > 1.5 x – 3.0 x baseline	Normal baseline: > 3.0 x – 10.0 x ULN Abnormal baseline: > 3.0 x – 10.0 x baseline	Normal baseline: > 10.0 x ULN Abnormal baseline: > 10.0 x baseline

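### The patient liver-safety table (Protocol Appendix 16.1) gives no action for an asymptomatic patient with a large ALT rise and bilirubin above 1x and up to 2x ULN, although the same ALT with normal bilirubin triggers action

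*Protocol*

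**What the plan says.** Protocol Section 7.4 lists liver criteria for the healthy-volunteer cohorts and, for patients with raised baseline ALT or AST, refers to Appendix 16.1. The appendix table has four rows, numbered here from the top. Each row combines an ALT threshold, a total bilirubin (TBL) condition and a symptom condition.

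- Row 1 (repeat liver tests in 2–3 days): "Normal baseline with treatment emergent (TE) increase to ALT > 5x ULN", or for raised baseline above 3x baseline or 300 U/L. TBL must be normal and symptoms absent.
- Row 2 (interrupt drug, close observation and workup): above 8x ULN for normal baseline, or "Elevated baseline with TE increase to: ALT > 5x baseline or > 500 U/L (whichever occurs first". TBL must be normal and symptoms absent.
- Row 3 (interrupt drug, close observation and workup): above 3x ULN for normal baseline, or "Elevated baseline with TE increase to ALT > 2x baseline or > 200 U/L (whichever occurs first". TBL must exceed 2x ULN and symptoms must be absent.
- Row 4 (interrupt, no restart): ALT thresholds as in row 3, TBL "Normal or elevated", with symptoms of clinical hepatitis.

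For healthy volunteers, Section 7.4 includes a criterion with no bilirubin condition: "Treatment emergent AST and/or ALT > 8X ULN which must be confirmed by repeat blood draw within 48 hours of initial results". The same section keeps a general power to act: "The Sponsor or PI can discontinue any patient at any time with or without DSC consultation".

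**The concern.** Between normal bilirubin and 2x ULN, the table has no row for a patient without symptoms. The rule therefore runs backwards over part of its range: as bilirubin rises past the upper limit of normal, the prescribed action disappears, and it returns only above 2x ULN.

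This matters because Section 5.7 names the ALT and AST stopping rules as a mitigation of hepatic risk in a first-in-human study of a liver-targeted drug, and Appendix 16.1 is the form those rules take for patients with raised baseline enzymes. Read literally, it prescribes repeat testing, or interruption with workup, for the milder liver profile and leaves the worse one to judgement. Row 2 also carries the restart condition, so a patient in the gap has no written restart criterion either.

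**Working it through.** The plan states no figure to reproduce. The check applies the four rows to every relevant combination.

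**Inputs.** The row conditions are those of Appendix 16.1 given above. *Normal* TBL is taken as ≤ 1x ULN. Assumed for illustration: baseline ALT 80 U/L and laboratory ALT ULN 40 U/L. The result does not depend on either, because the gap lies in the bilirubin column.

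**ALT thresholds at baseline 80 U/L** (whichever limit is reached first):
- Row 1: min(3 × 80, 300) = 240 U/L
- Row 2: min(5 × 80, 500) = 400 U/L
- Rows 3 and 4: min(2 × 80, 200) = 160 U/L

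**Rows met by an asymptomatic patient, baseline 80 U/L:**

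| ALT | TBL 0.9x ULN | 1.01x | 1.5x | 2.0x | 2.01x |
|---|---|---|---|---|---|
| 310 U/L (row 1 band) | 1 | none | none | none | 3 |
| 600 U/L (row 2 band) | 1 and 2 | none | none | none | 3 |

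A normal baseline of 35 U/L gives the same pattern: ALT 310 U/L (above 5 × 40 = 200) and ALT 350 U/L (above 8 × 40 = 320) meet no row at TBL 1.01x to 2.0x ULN.

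**Wider grid.** Baselines of 10 to 250 U/L in steps of 5 (49 values), ALT of 50 to 2000 U/L in steps of 10 (196 values) and TBL of 1.05x to 2.0x ULN in steps of 0.05 (20 values) give 49 × 196 × 20 = 192,080 asymptomatic points. None meets any row.

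**Tally.** Two ALT bands (row 1, row 2) by three TBL bands (normal; above 1x to 2x ULN; above 2x ULN) make 6 asymptomatic combinations, of which 2 are unmatched. ALT below the row 1 level is left out, because there the table plans no action with normal TBL either.

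**The reversal.** ALT 510 and 600 U/L both exceed the 500 U/L cap in row 2, so the contrast holds at any raised baseline: 510 U/L with normal TBL is interruption, 600 U/L with TBL 1.8x ULN is no row.

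**Severity of what is missed.** SAP Appendix A defines Grade 2 bilirubin as "Normal baseline: > 1.5 x – 3.0 x ULN", and Grade 1 as above ULN to 1.5x ULN. With normal baseline bilirubin, the gap therefore takes in all of Grade 1 and the part of Grade 2 up to 2x ULN. ALT 600 U/L is 600/80 = 7.5x baseline, Grade 3; this is so for any raised baseline below 600/5 = 120 U/L.

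**Reach.** Three cohorts of up to 6 give about 18 patients. In Table 2 the row "Labs (heme, coag, chem, lipase, lipids" is marked at 7 scheduled post-dose visits: 24 hours and Days 15, 29, 57, 71, 85 and 113. Two of these precede the Day 29 dose. Day 29 results can inform that dose only if they return before dosing, which is not stated.

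**The case against.** **Meaning of *Normal*.** The protocol does not define it for bilirubin, and the only elevation the table quantifies is above 2x ULN. One could read *Normal* as anything not above that level, and then there is no gap. This reading is strained: row 4 sets normal against elevated in the same column, and SAP Appendix A grades any value above ULN as increased. The column heading does refer to treatment-emergent bilirubin, so a stable, pre-existing mild elevation might be argued to stay in rows 1 and 2. That would narrow the gap to new rises without closing it.

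**Other safeguards.** Sections 7.4 and 8.4 allow discontinuation or withdrawal. Section 11.2 has clinically significant laboratory findings recorded as adverse events, and Section 11.6 requires follow-up with further investigation as indicated. The related-SAE and severe-reaction criteria are not confined to volunteers. All of this stands, but it rests on judgement; none of it sets an ALT and bilirubin threshold for patients.

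**The volunteer comparison.** The criterion above 8x ULN supports the argument only for row 2. Volunteers have no ALT-based criterion at 5x to 8x ULN with TBL up to 2x ULN and no symptoms or INR rise. This is correct and limits the comparison.

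**Size.** The appendix is headed as guidelines, the 2 of 6 counts table cells rather than patients, the SAP grades serve shift tables rather than dosing, and only one dose can be withheld. Cohort 1b enrols after 3b and 4b, so fewer than 18 patients may remain to be dosed. These points bear on the weight of the issue, and they do not make the table right.

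**Conclusion.** The concern holds. On the table's own wording, an asymptomatic patient whose ALT meets row 1 or row 2 and whose TBL is above 1x and up to 2x ULN meets no row, while the same ALT with normal bilirubin triggers action. That is 2 of the 6 asymptomatic combinations at or above the row 1 ALT level. The conclusion rests on reading *Normal* as not above ULN, which row 4 supports.

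The fault is in the written rule; the power to act remains. No endpoint or analysis changes. Interruption can affect only the Day 29 dose, whereas the repeat-testing and close-observation steps are relevant after all seven post-dose laboratory visits. The documents give no frequency for the combination, so no expected number of affected patients can be stated. It should be fixed, because a safety threshold should not lapse as the liver profile worsens and the correction is small.

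**What to change.** In Appendix 16.1, change the bilirubin entry in rows 1 and 2 from *Normal* to *≤ 2x ULN*, and leave rows 3 and 4 as they are. Row 3's ALT thresholds (3x ULN; 2x baseline or 200 U/L) lie below row 1's (5x ULN; 3x baseline or 300 U/L). Every asymptomatic patient above the row 1 level then meets row 1 or 2 at TBL ≤ 2x ULN, or row 3 above it, and unmatched combinations fall from 2 of 6 to 0 of 6.

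The cost is wording in two table cells. ALT and bilirubin are already part of the chemistry panel at each laboratory visit, so no test or visit is added. The downside is an occasional extra repeat test or a withheld Day 29 dose.

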# Guidelines for close observation for potential drug induced liver injury:

Within 72 hours, perform a symptom directed history, physical, and liver biochemistries, including evaluation of:

- New or worsening signs and symptoms of clinical hepatitis such as fatigue, nausea, vomiting, right upper quadrant pain or tenderness, fever, rash, or eosinophilia
- Concomitant medications, including acetaminophen, dietary supplements, herbal remedies, over-the-counter medications, recreational drug use, and special diets
- Alcohol consumption
- Exposure to environmental chemical agents
- Past medical history
- Complete review of systems
- Liver biochemistries including ALT, AST, alkaline phosphatase, total bilirubin, and INR

Evaluate patients for signs and symptoms of clinical hepatitis and obtain liver biochemistries until biochemistries stabilize.

If biochemistries stabilize and the subject is asymptomatic, monitor liver biochemistries once a week until they return to baseline.

Subjects who live far from study sites may be evaluated locally for history, physical exam, and laboratories, if the results are communicated promptly to the site investigator.

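### In Appendix 16.1 every liver rule for patients needs an ALT rise, so AST with raised bilirubin, or ALT/AST with INR above 1.5, does not by itself interrupt the Day 29 dose

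*Protocol*

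**What the plan says.** Protocol Section 7.4 (and the Synopsis) lists its laboratory liver criteria under a heading for the NHV cohorts. Two of them matter here: "A treatment emergent AST or ALT >3X ULN (must be confirmed on repeat) with a total bilirubin >2X ULN" and "A treatment emergent AST or ALT >3X ULN (must be confirmed on repeat) with an INR > 1.5". The INR criterion also asks for confirmation and for no other plausible cause. All of these are introduced as findings that may justify stopping.

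For patients the same section says only "See Appendix 16.1 for treatment modification guidelines in patients with baseline/pre-dose elevated ALT or AST".

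Appendix 16.1 has one transaminase column, for ALT, and four rows:

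- Row 1 (bilirubin normal, no symptoms): ALT above 5x ULN with a normal baseline, or above 3x baseline or 300 U/L with an elevated one. Action: repeat tests, no interruption.
- Row 2 (bilirubin normal, no symptoms): ALT above 8x ULN, or "Elevated baseline with TE increase to: ALT > 5x baseline or > 500 U/L (whichever occurs first". Action: interrupt.
- Row 3 (bilirubin above 2x ULN): ALT above 3x ULN, or "Elevated baseline with TE increase to ALT > 2x baseline or > 200 U/L (whichever occurs first". Action: interrupt.
- Row 4 (symptoms of hepatitis, any bilirubin): the same ALT limits as row 3. Action: interrupt and do not restart.

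For rows 2 and 3, "Study drug can be restarted only if an alternative etiology is identified and liver enzymes return to baseline". AST appears in the table only among the tests to repeat in row 1. AST and INR appear in the follow-up guidance only as measurements: "Liver biochemistries including ALT, AST, alkaline phosphatase, total bilirubin, and INR".

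**The concern.** Healthy volunteers receive one dose. Patients in Cohorts 1b, 3b and 4b receive a second on Day 29, so they are the only participants whose next dose a liver rule can withhold. Yet the two combinations that join AST to bilirubin, or either enzyme to INR, are written only for the volunteers. Raised bilirubin or symptoms lower the ALT limit in the patient table but never replace it, and INR does not enter at all.

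A patient could therefore show a transaminase rise together with a sign of impaired liver function and, on the table alone, be due for dosing on Day 29. An INR above 1.5 on study would normally be new, because exclusion criterion 18 bars it at screening and criterion 19 restricts anticoagulants.

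**Working it through.** The plan gives no figure to reproduce. The check is a reading of the table by row, then two worked cases.

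**Count.** Rows that need an ALT threshold: 4 of 4. Rows that AST alone can meet: 0 of 4. Rows that use INR: 0 of 4.

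**Inputs.** Row limits are from Appendix 16.1. For elevated baseline ALT = B, row 1 is ALT > min(3B, 300), row 2 is ALT > min(5B, 500), and row 3 is ALT > min(2B, 200). The laboratory ULN is not stated for these rows; I assume 40 U/L for both enzymes and show the range 30 to 55. Values are taken as confirmed, possibly related, otherwise unexplained and without listed symptoms.

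**Case 1: AST 400 U/L, ALT 110 U/L, bilirubin 2.5x ULN.**
- Rows 1 and 2 need normal bilirubin, so only row 3 can apply.
- Elevated baseline: 110 > 2B only if B < 110/2 = 55. At ULN 40, row 3 is met for B = 41 to 54 and no row is met for B of 55 or more.
- Normal baseline: row 3 needs ALT > 3 x 40 = 120, so it is not met. Since 110/3 = 36.7, this holds for ULN of 37 or more; at 30 to 36 row 3 is met.
- The NHV criterion is met throughout the range: 400 exceeds 3 x 55 = 165.
- With AST added to row 3, it would fire at normal baseline AST (400 > 165 even at ULN 55) and at elevated baseline AST below 400/2 = 200 U/L.

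**Case 2: baseline ALT 60, ALT 170 U/L, INR 1.7, bilirubin normal.**
- Row 1 needs > 3 x 60 = 180 and row 2 needs > 5 x 60 = 300. Neither is met, so not even repeat tests are ordered. This holds at any ULN from 30 to 55, because 60 is an elevated baseline throughout.
- The NHV limit of 3x ULN is 90 to 165 U/L over that range, so 170 exceeds it.
- A limit of 2x baseline (120) would be met.
- For ALT 170 at ULN 40 and other elevated baselines, a 2x-baseline row would fire for B = 41 to 84 (170/2 = 85). Today row 1 orders repeat tests for B = 41 to 56 (170/3 = 56.7), and no row applies for B = 57 to 84.

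**ALT needed to interrupt when INR is above 1.5, bilirubin is normal and there are no symptoms:**

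| Baseline ALT (elevated) | Now: min(5B, 500) | With a 2B row |
|---|---|---|
| 45 | > 225 | > 90 |
| 60 | > 300 | > 120 |
| 80 | > 400 | > 160 |
| 100 | > 500 | > 200 |
| 200 | > 500 | > 400 |
| 250 | > 500 | > 500 |

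Screening allows ALT up to 250 U/L (exclusion criterion 18), where the two limits meet. If row 3's 200 U/L cut-off were copied into the INR row, any ALT rise from a baseline of 200 to 250 would satisfy it, and INR alone would in effect decide. The new row should therefore have no absolute limit.

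**Timing.** Protocol Table 2 draws chemistry and coagulation at pre-dose, 24 hours and Day 15. With ±2-day windows, Day 15 (13 to 17) to Day 29 (27 to 31) leaves 27 − 17 = 10 to 31 − 13 = 18 days to repeat a value. A trigger first seen after the Day 29 dose withholds nothing.

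**Reach.** Section 7.1 enrolls Cohort 1b after 3b and 4b. It has up to 6 patients, or 6 + 2 = 8 with the Synopsis allowance, plus anyone in another cohort still to be dosed.

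**The case against.** The strongest reply is that patients are not left uncovered, and that stands. Rule 1 of Section 7.4 (one related SAE, or severe related reactions in two subjects of a cohort) is not limited to volunteers. Section 11.1 counts medically important events as SAEs, so Case 1 might qualify. Section 11.2 makes clinically significant laboratory values reportable as AEs, Section 8.4 lets the investigator withdraw a participant, the DSC may pause the study, and the sponsor or investigator may discontinue any patient. A reader might infer that patients have no liver protection; the documents do not support that. What these routes lack is a set threshold for the two patterns.

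A reader might also infer that the same values would force a halt in volunteers. They would not. The NHV criteria only say that stopping may be justified, and the one firm commitment, "enrollment and dosing in healthy volunteers will be paused pending a review of safety data", is worded for the serious or severe reactions of rule 1, not for laboratory values. A patient row that orders interruption is thus stricter than the volunteer criteria. The reason for it is the second dose, not parity.

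Nor do Section 5.7, which cites stopping rules for both enzymes, or the pointer in 7.4 contradict the appendix outright. Section 5.7 is true of the protocol as a whole, and the pointer says who uses the table, not what triggers it. The table is adapted from a publication on liver injury in pre-existing liver disease, so an ALT-led design may be deliberate; the protocol does not say.

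**Conclusion.** The gap is real and narrow. Appendix 16.1 is the only liver-specific dose-interruption rule for patients, and each row depends on ALT. Neither AST elevation with bilirubin above 2x ULN (ALT below its row 3 limit), nor ALT or AST elevation with INR above 1.5 (bilirubin normal, no symptoms, ALT below its row 2 limit), interrupts the second dose by itself. The row count needs no assumption; the worked cases rest on the assumed ULN of 40 U/L, with the range shown.

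The consequence is limited by the discretionary cover, by the small number still to be dosed, and by the requirement that the trigger appear before Day 29. A reader might want a probability that a dose would be withheld. The documents give no event rate, so none can be stated. This is a low-cost improvement to patient safety, not a flaw in the trial's analysis.

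**What to change.** In Appendix 16.1:

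1. In row 3 only, write ALT or AST, each judged against its own ULN (above 3x, normal baseline) or its own baseline (above 2x, elevated baseline). Keep the 200 U/L cut-off for ALT only.
2. Add a row: treatment-emergent ALT or AST above 3x ULN (normal baseline) or above 2x baseline (elevated baseline, no absolute U/L limit), with INR above 1.5, confirmed on repeat and not otherwise explained. Action: interrupt study drug and start close observation, with the restart condition of row 3.

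Leave rows 1, 2 and 4 as they are. Adding AST to rows 1 and 2 would admit isolated AST rises, including those of muscle origin, and row 4 bars restart; widening any of these is a separate trade-off. If AST and INR were left out on purpose, the appendix should say so instead.

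The cost is a short protocol clarification with no new test. The downside is an occasional Day 29 dose withheld, or delayed beyond its ±2-day window. A delay is a deviation and shortens the planned 71 − 29 = 42 days between second dose and biopsy. Either way a two-dose Day 71 biopsy as planned is lost in a cohort of up to 6 to 8.
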